## **1. SPECIFIC AIMS FOR THE PROTOCOL:**

Leptin is now an approved therapeutic in the form of Myalept in patients with generalized forms of lipodystrophy. However, it is still under investigation for patients with partial forms of the disease based on FDA decision on February 24, 2014. We have been conducting the clinical research protocol: "CLINICAL PROTOCOL to investigate the efficacy of recombinant human leptin (METRELEPTIN) in nonalcoholic steatohepatitis (NASH) or nonalcoholic fatty liver disease (NAFLD) associated with lipodystrophy (MB002-014)" under IND 72,734. All of patients enrolled on this ongoing protocol have partial lipodystrophy, specifically familial partial lipodystrophy.

We would like to create this novel protocol to allow continued treatment of patients with partial forms of lipodystrophy who volunteered and completed treatment under our ongoing protocols and who have derived significant clinical benefit as judged by an amelioration of their HbA1c, triglyceride levels, and/or reduction in their baseline diabetes or lipid therapies that affect quality of life.

**Therefore, our aim is to determine the long term safety and efficacy of Metreleptin (Myalept,) in promoting amelioration of metabolic abnormalities in patients with all forms of partial lipodystrophy. Patients who have completed University of Michigan research protocol MB002-014 and have shown improved clinical benefit as judged by clinical criteria set forth in this protocol will be offered the opportunity to participate in this new research study.**

The primary outcome measure will be percent change in fasting triglyceride levels. The hypothesis is that the triglyceride levels will not change during the follow up period. Secondary outcome measure will be percent change in HbA1c values again with the hypothesis that this will not change during the follow up period.

### **Exploratory outcomes:**

We will measure change in liver function tests, alanine aminotransferase (ALT) and aspartate aminotransferase (AST). We will also explore body weight, body composition, free fatty acid levels, and HOMA-IR.

## **2. PROTOCOL:**

*Study goal: We now would like to continue observation in patients who have exhibited significant clinical benefit who have demonstrated a significant clinical benefit and for whom other therapies have previously failed to provide adequate control in the absence of metreleptin. In order to accomplish this aim, we now propose an open-label prospective continued long-term study with recombinant human leptin therapy in patients with all forms of partial lipodystrophy. The goal of this study is to allow treatment of patients for long term and this study is designed more like an expanded access intention.*

### **2.1 STUDY DESIGN**

*Screening information: Patients will be evaluated at the time of completion of the parent study.*

## 2.2 INCLUSION AND EXCLUSION CRITERIA

### *Inclusion criteria for initial phase of the study:*

- Previously completed study protocol:
  - CLINICAL PROTOCOL to investigate the efficacy of recombinant human leptin (METRELEPTIN) in nonalcoholic steatohepatitis (NASH) or nonalcoholic fatty liver disease (NAFLD) associated with lipodystrophy, MB002-014 (IRMBED: HUM00058708)
- Demonstrates clinical benefit as defined by meeting at least one of the following criteria upon completion of the above stated protocols:
  - Reduction of HbA1c  $\geq$  1.0% or,
  - Reduction of triglycerides  $\geq$  30% of baseline or,
  - Decrease in insulin requirements  $\geq$  40% or,
  - Reduction in total NASH score by  $\geq$  2 points,
  - Significant worsening of metabolic parameters after discontinuation of Metreleptin if discontinuation has been undertaken.
  - A health condition that appears to have significantly improved by metreleptin for which two independent health care providers make a request to prevent drug discontinuation. In addition, the PI has to document absence of contraindications for drug continuation (such as bone marrow suppression).
- Is male or female  $\geq$  5 years old at baseline.
- Is male, female not of childbearing potential, or meets all the following criteria if female of childbearing potential (including perimenopausal women who have had a menstrual period within one year):
  - Not breastfeeding
  - Negative pregnancy test result (human chorionic gonadotropin, beta subunit [ $\beta$ hCG]) at baseline (not applicable to hysterectomized females).
  - Must practice and be willing to continue to practice appropriate birth control (defined as a method which results in a low failure rate when use consistently and correctly, such as implants, injectables, oral contraceptives, some intrauterine contraceptive devices, sexual abstinence, tubal ligation, or a vasectomized partner) during the entire duration of metreleptin treatment.
- Has physician-confirmed lipodystrophy as defined by evidence of partial (limbs) loss of body fat outside the range of normal variation.
- If  $\geq$  18 years of age, is able to read, understand and sign the U of M IRBMED approved informed consent form (ICF), communicate with study physician and study team, understand and comply with protocol requirements.
- If  $<$  18 and  $\geq$  7 years of age, is able to read, understand and sign the appropriate U of M IRBMED approved assent form and has a parent or legal guardian that is able to read, understand and sign the ICF.
- If  $<$  7 and  $\geq$  5 years of age or unable to read, the appropriate assent form must be explained to the child.
- If previously treated with thiazolidinediones or Vitamin E, stable dose of these medications for at least 3 months.

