*Treatment:* Up to fifteen patients will be enrolled into this long-term treatment extension study. Patients will be continued on metreleptin treatment as mentioned. This will be injected subcutaneously after reconstitution once a day in the morning at approximately the same time of the day that fits the subject's calendar. Dose may be titrated up to 15 mg daily based on metabolic response as needed.

*Follow-up schedule and monitoring:* Scheduled outpatient visits will occur at 6 month intervals. Tolerability will be assessed at each visit. During each visit, patients', weights, BMI, injection site inspection and basic laboratory data (comprehensive metabolic panel (fasting glucose, BUN, creatinine, sodium, potassium, chloride, CO2, calcium, total protein, albumin, total bilirubin, AST, ALT, alkaline phosphatase), fasting insulin, fasting leptin levels, fasting lipid panel (total cholesterol, triglycerides, HDL, LDL)), will be recorded. Throughout the study, lab work for CBC with differential count and creatinine kinase will be obtained at each visit.

Unscheduled visits may occur at more frequently than ever six months in order to follow-up on any adverse event or unanticipated health issues participants may be having.

*Study Termination:* Patient participation will be concluded five years after the patient's baseline appointment. At this time normal follow-up study procedures will be conducted, final drug accountability will be performed and patient will be transitioned to clinical care.

*Preparation for study visits:* Subjects will be asked to refrain from alcohol or tobacco use for 72 hours prior to the visit. They will report to the Research Center after 10 hours of fasting. They will be allowed to consume water overnight prior to the studies.

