## **2.3 EVALUATION OF PROCEDURES OF THE STUDY**

### **A. Metabolic evaluation of lipodystrophic patients with NASH or NAFLD (tests will be conducted after a 10 hour fast, will be done at each visit).**

1. Blood Chemistry: The following tests will be performed after an overnight fast: fasting glucose and insulin, fasting triglyceride levels, hemoglobin A1c, fasting free fatty acid levels, fasting total, HDL and LDL cholesterol, serum ALT, AST, albumin, alkaline phosphatase, bilirubin (direct and indirect), serum electrolytes, BUN and creatinine, calcium. The previously listed blood chemistry tests will be charged to the patient's insurance as standard, routine care procedures. Approximately 10cc of serum will be aliquoted and frozen for potential future tests.

2. Determination of insulin sensitivity using HOMA-IR: The homeostatic model assessment (HOMA) will be used as a surrogate estimate of insulin resistance based on fasting insulin and glucose concentrations and calculated as fasting insulin concentration (mU/L) x fasting glucose concentration (mmol/L)/22.5 (5).

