## B. Research sample

We will also collect and store samples for determination of TNF- $\alpha$  soluble receptor, TGF-B, FGF-21 and other potential markers.

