### **4.1 RISK ASSOCIATED WITH EVALUATION METHODS**

Risks with blood tests: The total amount of blood drawn from the patients will be kept within the IRB restrictions. Total amount of blood to be drawn with the outlined studies is estimated not to exceed 960 cc over the course of 12 months. Each blood draw is associated with pain and risks of infection though these risks are minimal.

Risks with study procedures: In this study, patients are asked to have 2 extensive visits in 12 months. In addition to the above risks some patients may find the time needed to complete the research studies an inconvenience in their routine lives. Each participant into the study will clearly understand that participation is totally voluntary.

Our research plans will be monitored by the University of Michigan IRB.

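### No pregnancy test is scheduled after baseline, although drug is re-dispensed every six months for five years and a discovered pregnancy ends treatment

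*Protocol*

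**What the plan says.** **Entry.** The inclusion criteria in Protocol section 2.2 ask females of childbearing potential for a negative beta-hCG "at baseline (not applicable to hysterectomized females"). They must also use effective contraception "during the entire duration of metreleptin treatment".

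**Follow-up.** Under the follow-up paragraph of 2.2, "Scheduled outpatient visits will occur at 6 month intervals". That paragraph itemises the bloods taken and adds that "lab work for CBC with differential count and creatinine kinase will be obtained at each visit". The termination paragraph says "Patient participation will be concluded five years after" the baseline appointment. Section 2.3 A gives a second each-visit list, introduced by "The following tests will be performed after an overnight fast". Section 2.3 B covers stored research samples ("We will also collect and store samples for determination of" several markers).

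**Drug supply.** Table 1 in the Appendix marks distribution of study medication at baseline, at six-monthly follow-up and at unscheduled visits. Section 3.3 has patients inject themselves.

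**If pregnancy occurs.** It is a ground for removal (4.4), is handled as a serious adverse event (5.3), is reportable to the drug supplier within 24 hours (5.4) and ends treatment permanently once found (5.9). Exposure in pregnancy is reportable as a special situation (5.7). Section 6 excludes pregnant women, but only from enrollment.

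**The concern.** The protocol treats pregnancy as an event that stops the drug and triggers urgent reporting. Each of those rules starts when someone learns of the pregnancy, and no scheduled procedure in the available text is designed to find it out. The dispensing visit is the obvious control point: the patient is on site, blood is being drawn, and the next supply is about to be handed over.

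As written, a patient with an unrecognised pregnancy can leave that visit with more drug, and the discontinuation rule never starts. Entry from age 5 with five years of participation adds a possible case: a girl could reach childbearing potential during the study with no test ever required of her. The protocol does not show that any such patient is enrolled.

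The point is about patient safety and the visit schedule. It does not touch an endpoint, the sample size or an analysis. A visit schedule belongs in the protocol, so this is not something to leave to a statistical analysis plan.

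**Working it through.** The protocol gives no figure to reproduce here. The check sets its lists side by side and counts visits.

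**1. Is hCG in any each-visit list?**

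| Source | Content | Pregnancy test |
|---|---|---|
| 2.2, inclusion criteria | beta-hCG at baseline | yes, baseline only |
| 2.2, follow-up paragraph | 14 metabolic-panel analytes + insulin + leptin + 4 lipids + CBC with differential + creatinine kinase = 22 | 0 |
| 2.3 A, blood chemistry | glucose, insulin, triglycerides, HbA1c, free fatty acids, cholesterol fractions, liver tests, electrolytes, renal function, calcium | 0 |
| 2.3 B, research samples | cytokine and growth-factor markers | 0 |
| Appendix, Table 1 | 9 rows | 0, not even at baseline |

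Table 1 has a fasting biochemistry row that could in principle be read broadly, but 2.3 A spells out the blood chemistry without hCG. Because Table 1 also leaves out a test that 2.2 requires, its silence is weak evidence by itself. The itemised lists in 2.2 and 2.3 are stronger.

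**2. How many scheduled dispensings have no test?**

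- Visit frequency: section 4.1 says "patients are asked to have 2 extensive visits in 12 months", which agrees with the six-month interval in 2.2.
- Follow-up visits: 2 per year × 5 years = 10 (months 6, 12, …, 60).
- Month 60 is the termination visit, with final drug accountability, so re-dispensing visits = 10 − 1 = 9 (months 6 to 54).
- Scheduled pregnancy tests at those 9 visits: 0.
- Last scheduled test (month 0) to last scheduled re-dispensing (month 54): 54 − 0 = 54 months. With a test before each dispensing, this becomes 0.

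The 54 months is a gap between scheduled events. It does not measure exposure.

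**3. Upper bound on added testing.**

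- Up to 15 patients × 9 visits = 135 assays.
- With an optional month-60 test: 15 × 10 = 150.

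Both assume that every patient is a female of childbearing potential who stays for five years, and both count scheduled visits only. The protocol gives no sex or age split and no quantity dispensed per visit, so neither a number of pregnancies nor an amount of exposure can be estimated.

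**The case against.** The strongest reply is that this argues from silence in lists that are demonstrably incomplete. The follow-up list in 2.2 omits HbA1c, which is the secondary outcome, and free fatty acids; both appear in 2.3. The list in 2.3 omits CBC, creatinine kinase and leptin; all three appear in 2.2. Serum kept for antibody testing is mentioned only in 4.2. A test missing from one list may therefore still be intended. Part of 4.2 and the consent pages were not available, and pregnancy precautions could sit there.

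The reply continues that the existing scheme is coherent (baseline test, contraception throughout, removal, rapid reporting, permanent discontinuation) and that no text promises repeat testing. The available risk text names no fetal toxicity, the study takes at most 15 patients, and unscheduled visits allow testing on suspicion. Six-monthly testing would still leave a pregnancy conceived just after a visit undetected by schedule for nearly six months.

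Much of this stands as a limit on the claim. The harm is not quantified, exposure between visits would remain, and repeat testing may be mentioned in text not seen here. None of it supplies a scheduled test. The items missing from one of the two main laboratory lists are found in the other, whereas hCG is in neither. If repeat testing is described in 4.2 or the consent form, the visit lists and Table 1 would still need to carry it, because staff work from those. Contraception is defined in 2.2 by a low failure rate, not a zero one, and 4.4 and 5.9 themselves anticipate pregnancies on study. Testing on suspicion does not help when the pregnancy is unsuspected.

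**Conclusion.** The concern holds on the available text. The protocol schedules one pregnancy test, at baseline, followed by nine scheduled re-dispensing visits over 54 months with none, while its stopping and reporting rules depend on a pregnancy being known. Table 1 separately fails to show the baseline test that the inclusion criteria require, and that needs correcting whatever is decided about repeat testing.

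The change should be made but is not critical: other safeguards exist, the study is small, and no number of affected patients can be derived. The conclusion assumes that the lists in 2.2 and 2.3 describe what is done at follow-up, and that drug is handed out at each follow-up visit as Table 1 marks. Confidence is medium because part of 4.2 and the consent pages were not seen.

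**What to change.** - Add beta-hCG for females of childbearing potential to the visit bloods in 2.2 and 2.3, at baseline and at each six-monthly visit where drug is dispensed.
- Add a pregnancy-test row to Table 1 with the same timing, including baseline.
- Require the result to be seen before drug is released. Use serum from blood already drawn, or a urine test where no same-day serum result is available.
- Reassess childbearing potential at every visit, and apply both the test and the contraception requirement from the visit at which it is reached.
- A test at the month-60 termination visit is optional.

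**Cost.** At most 135 added assays over the study (150 with month 60), at visits that already take place, and a short amendment of 2.2, 2.3 and Table 1. The downside is a small assay cost and an occasional false positive that needs a repeat test and delays dispensing. The gain is a check before each scheduled re-supply.

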### *Exclusion criteria:*

- Presence of advanced liver disease (as evidenced by abnormal synthetic function, abnormal PT or albumin).
- Evidence of other etiologies of viral hepatitis.
- Presence of clinically significant hematologic abnormalities (such as neutropenia and/or lymphadenopathy).
- Presence of HIV infection.
- Inability to give informed consent.
- Presence of ESRD, any type of active cancer, or  $>$ class 2 congestive heart failure ((New York Heart Association Functional Classification System), based on medical history and physical examination).

### *Study Inclusion:*

Criteria for continuation into the long-term phase is based solely on proven clinical benefit using criteria universally accepted to be beneficial. The following criteria are accepted as evidence of substantial clinical benefit upon completion of CLINICAL PROTOCOL to investigate the efficacy of recombinant human leptin (METRELEPTIN) in nonalcoholic steatohepatitis (NASH) or nonalcoholic fatty liver disease (NAFLD) associated with lipodystrophy, MB002-014 (IRMBED: HUM00058708):

- Reduction of HbA1c  $\geq$ 1.0% or,
- Reduction of triglycerides  $\geq$ 30% of baseline or,
- Decrease in insulin requirements  $\geq$ 40% or,
- Reduction in total NASH score by  $\geq$ 2 points.
- Significant worsening of metabolic parameters after discontinuation of Metreleptin if discontinuation has been undertaken.

- A health condition that appears to have significantly improved by metreleptin for which two independent health care providers make a request to prevent drug discontinuation. In addition, the PI has to document absence of contraindications for drug continuation (such as bone marrow suppression).

*Study group:* We will enroll up to a total of up to 15 subjects to receive study drug Metreleptin from our parent studies.

*Restorative leptin therapy:* This is defined as administration of recombinant methionyl-human leptin subcutaneously to achieve high normal levels of circulating leptin in individuals who started out with lower than normal or low normal levels of circulating leptin(1, 2). Recombinant human leptin will be provided by Amryt Pharma (Boston, MA). Previous experience from patients with lipodystrophy or with congenital absence of leptin indicates that this goal can be achieved by administration of 0.02 to 0.10 mg/kg/day in adult males depending on baseline leptin concentrations and body surface area of the patients. In this study, patients will be treated with 2.5 and 5 mg /day (male and female respectively) to achieve high physiological concentrations. Higher dose titrations can be used in the judgment of the PI as indicated up to 10 mg daily. It is important to note that the patients enrolling in this long term study will be on metreleptin therapy that has been found effective, therefore, their dose will likely not change during this protocol. .

*Treatment:* Up to fifteen patients will be enrolled into this long-term treatment extension study. Patients will be continued on metreleptin treatment as mentioned. This will be injected subcutaneously after reconstitution once a day in the morning at approximately the same time of the day that fits the subject's calendar. Dose may be titrated up to 15 mg daily based on metabolic response as needed.

*Follow-up schedule and monitoring:* Scheduled outpatient visits will occur at 6 month intervals. Tolerability will be assessed at each visit. During each visit, patients', weights, BMI, injection site inspection and basic laboratory data (comprehensive metabolic panel (fasting glucose, BUN, creatinine, sodium, potassium, chloride, CO2, calcium, total protein, albumin, total bilirubin, AST, ALT, alkaline phosphatase), fasting insulin, fasting leptin levels, fasting lipid panel (total cholesterol, triglycerides, HDL, LDL)), will be recorded. Throughout the study, lab work for CBC with differential count and creatinine kinase will be obtained at each visit.

Unscheduled visits may occur at more frequently than ever six months in order to follow-up on any adverse event or unanticipated health issues participants may be having.

*Study Termination:* Patient participation will be concluded five years after the patient's baseline appointment. At this time normal follow-up study procedures will be conducted, final drug accountability will be performed and patient will be transitioned to clinical care.

*Preparation for study visits:* Subjects will be asked to refrain from alcohol or tobacco use for 72 hours prior to the visit. They will report to the Research Center after 10 hours of fasting. They will be allowed to consume water overnight prior to the studies.

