**Amryt representative: [name]**

**Sr. Supply Chain Manager**

**Amryt Pharma PLC**

**[contact]**

### 3.3 DRUG DOSAGE AND ADMINISTRATION

Metreleptin will be administered by subcutaneous injection at the doses specified above. Subjects will be instructed by study personnel to reconstitute the medication and self-administer the injections and will perform the first injection under the supervision of study personnel.

The dosing recommendations for Metreleptin are listed below:

Body Weight	Gender	Daily Recommended Metreleptin Dose
≤40 kg	Male	0.06 mg/kg
	Female	
>40 kg	Male	2.5 mg (0.5 mL)
	Female	5.0 mg (1.0 mL)

Initial Metreleptin dose may be adjusted based upon the subject's dose at termination of the two previous studies for reasons of efficacy. Metreleptin dose may be adjusted at investigator's discretion based on clinical response (e.g. inadequate metabolic control or excessive weight loss or tolerability issues). Injections at a single site will have a maximum allowable volume of 2.0 ml. Preferably study medication will be administered at approximately the same time each day. Drug administration will occur once a day (QD). Metreleptin administration may be changed to twice a day (BID) at investigator's discretion based on clinical response (e.g. inadequate metabolic

control, tolerability issues). Dose exceeding 1.0 mL may be administered as two separate injections in order to minimize patient discomfort due to injection volume. Metreleptin dose can be injected into the abdomen, upper arm or thigh region depending on patient preference and comfort. The site(s) of injection will not occur on the limb from which subsequent blood draws will occur that day.

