## **6. WOMEN, MINORITY AND CHILDREN INCLUSION IN CLINICAL RESEARCH**

**1. Inclusion of Women:** The use of pregnant women is not the central focus of this research. Pregnancy, women who think they may be pregnant, women who are actively trying to conceive, and women who are currently breast-feeding are exclusion criteria for enrollment in this study. The general informed consent documents will advise sexual abstinence or use of contraception for female participants of child bearing age. The use of metreleptin is intended to provide direct benefit to women participating in this trial. There are no other accepted medical treatments that are likely to provide the same benefit.

**2. Inclusion of Minorities:** In our study, all patients with physician confirmed lipodystrophy and ultrasound confirmed non-alcoholic fatty liver disease will be recruited regardless of race and ethnicity. We will continue to do every effort to recruit minorities. If the number of minorities seems to be disproportionately low, we will ask for help from the MCRU Minority Recruitment Board.

**3. Inclusion of Children:** Subjects < 5 years old will not be included in this study as they would require a pediatric expertise not available at this study location. Subjects ≥ 5 years old will be included in this study as NAFLD in lipodystrophic patients is a rare disease with no other approved option for treatment. Liver biopsies are considered to be standard of care treatment for lipodystrophic patients and therefore these juvenile patients will not be placed at an unacceptable risk by having two liver biopsies performed as part of this research study. In this protocol's parent study and **in an ongoing study, FHA101, four pediatric patients have been successfully and safely treated with metreleptin.**

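### The protocol gives three daily-dose statements that disagree for eligible patients of 40 kg or less, and does not say which governs

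*Protocol*

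**What the plan says.** The protocol states the daily dose in three places.

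- **Section 2.2, paragraph on restorative leptin therapy:** "In this study, patients will be treated with 2.5 and 5 mg /day (male and female respectively"). No weight condition is attached. The paragraph allows titration to 10 mg daily. It adds that patients arrive on a dose already found effective: "therefore, their dose will likely not change during this protocol".
- **Section 3.3:** it opens with "Metreleptin will be administered by subcutaneous injection at the doses specified above" and then gives its own table. At 40 kg or less the dose is 0.06 mg/kg for both sexes. Above 40 kg it is 2.5 mg for males and 5.0 mg for females. It also says: "Initial Metreleptin dose may be adjusted based upon the subject's dose at termination of the two previous studies for reasons of efficacy". Later changes are left to the investigator's discretion.
- **Appendix, Protocol Table 1:** 5.0–10.0 mg/day at every visit, in a row labelled mg/kg/day, with no sex or weight condition.

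The treatment paragraph of Section 2.2 also gives a second titration limit, 15 mg daily.

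On who can enrol, the inclusion criteria set the minimum age at "5 years old at baseline" and include an assent rule for children aged 5 to under 7. Section 6 confirms the intention: "Subjects ≥ 5 years old will be included in this study as NAFLD in lipodystrophic patients is a rare disease".

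**The concern.** For a patient of 40 kg or less, Section 2.2 and Section 3.3 give different daily doses, and each is written as current, operative text. The back-reference that opens Section 3.3 does not help, because it points to the flat doses just before a table that departs from them. The Appendix schedule, which study staff may well consult at a visit, agrees with neither in this band. It also conflicts with the 2.5 mg male dose at any weight.

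Two things are at stake. The study team has no single reference dose for a small child, which is a safety matter. It also has no single dose against which to judge whether such a child was treated according to protocol, in a study whose stated aim is long-term safety and efficacy.

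**Working it through.** The protocol states no dose ratio, so there is no figure of its own to reproduce. The check is direct arithmetic.

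**Inputs**
- Flat dose (Section 2.2): 2.5 mg/day male, 5 mg/day female.
- Weight-based dose at 40 kg or less (Section 3.3): 0.06 mg/kg/day, both sexes.
- Appendix Table 1: 5.0–10.0 mg/day, no conditions.
- Body weight: not in the protocol. Assumed values of 15, 20, 30 and 40 kg are used to show the range.

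**Formulas**
- Weight-based dose = 0.06 × weight.
- Ratio = flat dose ÷ weight-based dose.

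| Assumed weight | Section 3.3 dose | Boy: 2.5 mg ÷ that dose | Girl: 5 mg ÷ that dose |
|---|---|---|---|
| 15 kg | 0.06 × 15 = 0.9 mg | 2.8 | 5.6 |
| 20 kg | 0.06 × 20 = 1.2 mg | 2.1 | 4.2 |
| 30 kg | 0.06 × 30 = 1.8 mg | 1.4 | 2.8 |
| 40 kg | 0.06 × 40 = 2.4 mg | 1.04 | 2.1 |

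The two rules would coincide at 2.5 ÷ 0.06 = 41.7 kg for males and 5 ÷ 0.06 = 83.3 kg for females. Both weights lie above 40 kg, so within the band the flat dose is always the larger. For boys the gap nearly closes at the top of the band. For girls it never falls below about twofold.

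**Third version.** The lower end of the Appendix range, 5.0 mg, equals the flat female dose. Set against Section 3.3, it therefore gives the ratios in the last column for either sex. For a male above 40 kg, where Sections 2.2 and 3.3 agree on 2.5 mg, the Appendix minimum is 5.0 ÷ 2.5 = 2 times that dose.

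**Titration limits.** Section 2.2 gives 10 mg in one paragraph and 15 mg in another. Neither says whether it applies at 40 kg or less.

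**The case against.** The strongest defence is that this is an extension study. Entrants have completed the parent protocol and will mostly continue the dose they were on. Section 3.3 calls its table recommendations, lets the starting dose follow the earlier one, and leaves adjustment to the investigator. For most patients neither figure is a fresh starting dose. This stands as a reason to expect a smaller practical effect. It does not resolve the conflict: the carry-over wording is only a likelihood in one place and a permission in the other. The inclusion criteria also admit patients whose drug had been discontinued, who may have no current dose to carry over.

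A second defence is that Section 2.2 is an adult summary. The sentence before the flat doses concerns adult males, and the rows above 40 kg in Section 3.3 repeat the same figures. That reading is reasonable, but the protocol does not state it, and it leaves the Appendix unexplained.

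Third, the affected group may be very small. Enrolment is capped at 15. The remark in Section 6 that "in an ongoing study, FHA101, four pediatric patients have been successfully and safely treated with metreleptin" pools that study with the parent study and gives no weights. So the documents show that such patients are eligible, not that any will enrol.

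A reader might also infer several stronger points that the documents do not support:
- **Different sites dosing the same child differently.** The protocol describes one centre, so the issue is two readings by one team.
- **The overdose reporting rule cannot be applied.** Section 5.10 defines overdose by a judgement that the dose is excessive and medically important, which does not depend on either dose statement.
- **Fourfold is the maximum gap.** It describes a girl of about 20 kg, which is an assumed weight. The ratio is 5.6 at 15 kg, and much smaller for boys.
- **The 10 or 15 mg limits, divided by the 0.06 mg/kg dose, measure the conflict.** That compares a ceiling with a recommended dose, and ceilings exceed recommended doses by design.

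**Conclusion.** The point holds as a contradiction in the current text. For eligible patients of 40 kg or less, Section 2.2, Section 3.3 and Appendix Table 1 do not give the same daily dose, and nothing says which prevails. Over assumed weights of 15 to 40 kg, the Section 2.2 dose is 2.8 down to 1.04 times the Section 3.3 dose for boys, and 5.6 down to 2.1 times for girls. These ratios rest on assumed weights; the contradiction itself does not. The Appendix conflict with the 2.5 mg male dose and the two titration limits extend the inconsistency beyond the low-weight band. How many patients are affected is unknown and may be few. No view is taken on which dose or limit is right.

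**What to change.** Reconcile the two dosing paragraphs of Section 2.2 (restorative leptin therapy and treatment), Section 3.3 and Appendix Table 1 into one governing dose statement that includes the weight bands. Have the other places refer to it instead of restating doses, and remove the back-reference at the start of Section 3.3. Correct the unit mismatch in the Appendix row. State how a dose carried over from the parent study relates to the governing statement. State whether a titration limit applies at 40 kg or less and, if so, which one. The sponsor must settle the dose and the limit.

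The cost is a wording amendment to Sections 2.2 and 3.3 and the Appendix, with no new procedures, visits or patients.
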